14.13.4. Non inclusion

All documents relating to the selected patients (consent, test results) but not included will be retained by the investigator and managed in the same manner than the patient documents included in the study.

14.13.5. Wrong inclusion

Any wrong inclusion will be discussed with the study monitor. The patient should be out of the study and replaced by another patient. All available data will be retained for tolerance analysis.

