7. CONCOMITENT TREATMENTS

All drug treatments taken by patients and any modifications during the study are allowed but must be documented. All physical treatments for lymphedema other than those prescribed in the protocol are prohibited and will result in exclusion from the study.

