13.2. PROTOCOL DEVIATIONS AND ANALYSIS PLAN

All cases of deviations from the protocol will be managed according to CEN Biotech's Standard Operating Procedures.

A detailed statistical analysis plan, based mainly on this paragraph of the study protocol, and in accordance with CEN Biotech statistical procedures, will be developed. This analysis plan will be validated by the Medical Director of medi France.

A data validation plan will first focus on defining a position when considering protocol deviations and thus define the analysis populations (Intent to Treat and Per Protocol). The analysis plan will specifically identify the statistical tests, analysis procedures, treatment of missing data considered, and the primary and secondary endpoints that will be used.

Will be considered as major deviations (patient excluded from per protocol analysis) wrong inclusions (non-compliance with the inclusion criteria and non-inclusion) and the absence of data concerning the main criterion of analysis. All other cases will be considered *a priori* as minor deviations.

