13.3. ANALYZED POPULATIONS

The populations analyzed are defined as follows:

- The "Intention to treat" population (ITT) will include all patients who have applied at least once the products under study subject of this research;
- The population "per protocol" (PP) will include all patients with no major deviation from the protocol.

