14.13.3. Stopping the study by the patient

Any patient wishing to leave the study for any reason can do so at any time.

In all cases, the investigator should seek to review the patient as soon as possible for a complete final evaluation in order to:

- know the motivation of the decision and mention it on the observation notebook;
- evaluate the clinical condition of the patient;
- if necessary, take the appropriate therapeutic measures: management of a side effect or an intercurrent pathology, prescription of another treatment.

Patients will stop treatment before the end of the study in the case of the occurrence of a serious pathology justifying the prescription of treatments not authorized by the protocol, or incompatible with the continuation of the study, and will come out prematurely of the trial.

The study monitor will be notified by telephone or fax, and a letter or report explaining this study discontinuation will be sent to him as soon as possible.

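### 14.13.5 conflicts with 13.2 and 13.3 on whether wrong inclusions count for efficacy, and no section requires a DD+30 volume from patients removed under 14.13.5 or section 7

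*Combined protocol and SAP*

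**What the plan says.** **Wrong inclusions.** Section 14.13.5 says "The patient should be out of the study and replaced by another patient" and then "All available data will be retained for tolerance analysis". It does not mention efficacy. Section 13.2 treats the same patients as follows: "Will be considered as major deviations (patient excluded from per protocol analysis) wrong inclusions". Section 13.3 defines ITT as the set that "will include all patients who have applied at least once the products under study subject of this research", with no exception for wrong inclusions.

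**Other physical treatment.** Section 7 says "All physical treatments for lymphedema other than those prescribed in the protocol are prohibited and will result in exclusion from the study". In 13.2 the only major deviations are wrong inclusion and absence of primary-criterion data, so using a prohibited treatment is in itself a minor deviation.

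**Measurement after leaving.** Section 9 schedules arm volume at D0, D5, DD+30 and DD+90, and says nothing about patients already out of the study. The only exit assessment is in 14.13.3, under stopping by the patient: "In all cases, the investigator should seek to review the patient as soon as possible for a complete final evaluation". Its listed aims are the reason for leaving, the clinical condition and any therapeutic measures.

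**Analysis.** Section 13.4.2 compares 20% responders at DD+30 by Chi2 and names no population. Section 13.2 leaves "treatment of missing data considered" to a later analysis plan, and says a data validation plan will take a position on deviations and "thus define the analysis populations (Intent to Treat and Per Protocol").

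**The concern.** Both rules act after randomisation, and both can cost the trial a primary-endpoint value that no later analysis plan can recover.

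For wrong inclusions, a site following 14.13.5 stops following the patient and enrols another. A statistician following 13.3 expects her in ITT. Replacement restores the head count but not the randomised comparison. Wrong inclusion need not be related to outcome, so the issue here is mainly who is counted and whether the value exists.

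Section 7 exclusion is different. Other physical treatment is plausibly sought when swelling returns, so exclusion may be related to outcome. The trial is open label, and night treatment in the control arm is only optional (section 9), so exclusion rates could differ by arm. That is a risk and not a documented fact. If such patients have no DD+30 value and the test uses observed values only, the response rates can be distorted.

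**Working it through.** **1. The plan's own figures.** Inputs from 13.1: response 0.75 v 0.50, two-sided alpha 0.05, power 80%. The mean rate is 0.625, so

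n = [1.960 × √(2 × 0.625 × 0.375) + 0.842 × √(0.75 × 0.25 + 0.50 × 0.50)]² / 0.25² = 57.7, rounded up to 58 per group.

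This matches the plan; the 0.25 v 0.50 in the software table gives the same n by symmetry. The 15% allowance gives 58 / 0.85 = 68.2, stated as 68. Section 5.3 raises 136 to 140, or 70 per arm, where power is about 87%. The point does not rest on a wrong sample size.

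**2. The sections side by side.**

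| Patient | Follow-up | Analysis set | DD+30 volume required? |
|---|---|---|---|
| Wrong inclusion, product applied | Out and replaced (14.13.5) | Out of per protocol (13.2); in ITT (13.3); only tolerance named (14.13.5) | No |
| Used other physical treatment | Excluded from the study (7) | In ITT (13.3); minor deviation, so also per protocol if the endpoint exists (13.2) | No |

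In both rows 13.3 includes the patient while the rule that removes her does not secure her endpoint. The exit review in 14.13.3 does not fill the gap: it is not tied to DD+30 and does not name arm volume.

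**3. Illustration for section 7 exclusions only.** The documents give no exclusion rates, so these are assumed. A share e of an arm is excluded, all are non-responders, and all are left out of the test. The apparent response rate is then p / (1 − e). With p = 0.50: e = 5% gives 52.6%, 10% gives 55.6%, 15% gives 58.8%. Simulation used 70 per arm, an uncorrected two-sided Chi2 at 0.05 and 1,000,000 runs. The type I columns assume 50% response in both arms; power assumes 75% v 50%.

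| e, circaid/control | Bias under the null (points) | False win, circaid | False win, control | Type I error | Power |
|---|---|---|---|---|---|
| 0% / 0% | 0 | 2.6% | 2.6% | 5.1% | 87% |
| 5% / 5% | 0 | 2.6% | 2.6% | 5.1% | 90% |
| 5% / 10% | −2.9 | 1.1% | 5.2% | 6.3% | 82% |
| 10% / 5% | +2.9 | 5.2% | 1.1% | 6.3% | 97% |
| 0% / 15% | −8.8 | 0.2% | 17.1% | 17% | 51% |

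The last row is an extreme case: 15% is the plan's whole allowance for losses, here placed entirely in one arm and entirely on non-responders.

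**4. Cost of keeping wrong inclusions.** Assume 5% of each arm are wrong inclusions who respond at 50% in both arms and whose volumes are measured. The circaid rate becomes 0.95 × 0.75 + 0.05 × 0.50 = 0.7375. Power at 70 per arm falls from about 87% to 83%. At 2% the rate is 0.745 and power is 85%.

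**The case against.** The best reply is that 14.13.5 sits among the administrative stopping rules, says data are kept for tolerance without saying that this is their only use, and never mentions ITT. On that reading 13.2 and 13.3 settle the analysis set and there is no clash of analysis rules. The reading is fair, and it rules out the stronger inference that the protocol orders wrong inclusions out of the ITT efficacy analysis. It still leaves them in ITT without a required DD+30 volume.

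Second, the exit review in 14.13.3 applies in all cases, and that section also covers patients leaving because a serious pathology needs treatments the protocol does not authorise. So the review may reach beyond voluntary withdrawal. That stands, but its timing is still not DD+30 and volume is not named.

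Third, a reader might infer that nothing fixes the populations or the missing-data rule, or that the protocol prescribes an observed-only test. The documents support neither. Section 13.2 defers both matters to later plans, and 12.4 requires a validation committee and a database freeze before the data go to the biometrics department. An observed-only test is just one result that the silence allows. What remains is narrower: 13.2 does not say when the missing-data rule is fixed relative to the interim analysis permitted by 13.4.4.

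Fourth, few patients should be lost because 13.3 requires at least one application, since treatment starts at D0. That is correct, and this part is minor.

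**Conclusion.** The point holds as a gap and an inconsistency in the text. 14.13.5 needs reconciling with 13.2 and 13.3, and DD+30 volume is not required from patients removed under 14.13.5 or section 7. Confidence is high on the text. The size and direction of any bias are unknown.

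Two stronger readings should be avoided. The bias figures describe assumed section 7 exclusions and say nothing about bias from wrong inclusions. The 17% type I error also does not mean a 17% chance of a false claim for the device: with more control exclusions, almost all of it is false wins for control, and false wins for circaid fall below their nominal share. Only the reverse imbalance favours the device (5.2% false wins at 10%/5%). All of this assumes that every excluded patient is a non-responder and is left out of the test. Mild imbalance matters little.

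It is worth correcting because an endpoint that was never measured cannot be recovered later, and the remedy is cheap.

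**What to change.** 1. **14.13.5, with 13.2 and 13.3.** State that wrong inclusions stay in the ITT efficacy analysis in the arm assigned and leave per protocol only. Any replacement is additional.
2. **14.13.5 and section 7.** State in both that leaving the study treatment or being excluded does not end data collection, so the existing DD+30 and DD+90 volumes are still measured in patients who consent. The prohibition in section 7, and any decision on continuing the device, are left to the protocol. State also how a wrong inclusion is handled if the endpoint in 8.1 cannot be defined, for example without a healthy contralateral limb.
3. **13.3 and 13.4.2.** Define ITT as all randomised patients in the arm assigned, and name that set for the primary test.

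Secondary, for the analysis plan: fix the missing-data rule before outcomes are compared, including before any interim analysis under 13.4.4.

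The cost is wording, since the visits already exist, plus the dilution shown in step 4 of the working. If 4 replacements per arm are added in the 5% case (74 per arm), power recovers to between 85% and 86%.

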14.14. QUALITY INSURANCE

The study will be performed in accordance with Good Clinical Practices and Standard Operating Procedures of CEN Gestion.

14.15. AUDIT AND INSPECTION

The investigator and the promoter agree to be audited by the Clinical Quality Insurance department of the promoter or of any person mandated by it and, if necessary, eventually being inspected by ANSM.

In all cases, the investigator accepts direct access to all data source to ensure the authenticity of the data.

14.16. CLINICAL REPORT

The clinical trial report, including a reminder of the objectives and methods, a presentation of the results and their discussion, will be written according to the ICH3 recommendations and submitted for approval, before signature, to the coordinator-investigator and the statistician who carried out the study analysis.

